Children with ASD were randomly separated into two groups: one receiving laser-acupuncture (LA) group (n=60) and the other sham laser-acupuncture (SLA) group (n=56), matched by age and severity of autism. The LA group received laser-acupuncture for selected acupoints while the SLA group received sham laser-acupuncture. A total of 24 LA and SLA sessions over 12 weeks were given. Primary outcome measures included Functional Independence Measure for Children (WeeFIM), Pediatric Evaluation of Disability Inventory (PEDI), Leiter International Performance Scale- Revised (Leiter-R), and Clinical Global Impression- Improvement (CGI-I) scale. Secondary outcome measures consisted of Aberrant Behavior Checklist (ABC), Ritvo-Freeman Real Life Scale (RFRLS), Reynell Developmental Language Scale (RDLS), and a Standardized Parental Report. Data were analyzed by the Mann-Whitney test.

RESULTS: There were significant improvements in the language comprehension domain of WeeFIM (p=0.02), self-care caregiver assistant domain of PEDI (p=0.028), and CGI-I (p=0.003) in the LA group compared to the SLA group. As for the parental report, the LA group also showed significantly better social initiation (p=0.01), receptive language (p=0.006), motor skills (p=0.034), coordination (p=0.07), and attention span (p=0.003).

ADDITIONAL SUPPORTIVE INFORMATION

Presently, several other alternative therapies that operate on similar application and scientific method of action and operation principles as the proposed Erchonia® HLS Laser Device therapy and apply energy to the scalp region to effect improvement in the symptoms of autistic disorder are readily being evaluated through both feasibility and controlled pivotal trials. These alternative therapies also apply stimulation to the scalp region, although most are in direct contact with the scalp and provide stronger impulses and energy to the region than occurs with the Erchonia® HLS which is also not in direct contact with the scalp, with no safety issues having been reported.

Among these alternative treatment modalities, the 4 primary ones identified are the following:

- 1) Repetitive Transcranial Magnetic Stimulation (rTMS): rTMS is a technique used in cognitive neuroscience research as well as in therapeutic approaches in certain neurological and psychiatry diseases to affect brain activity. It consists of applying a magnetic impulse to the brain through the scalp by placing an electromagnetic coil on the surface of the scalp. The electromagnetic coil produces high current pulses that induce an electrical field in the underlying brain tissue that is proposed to modify activity of those neurons inside the magnetic field and induce an electrophysiological change in the target area. When the induced field is above a certain threshold and is directed in an appropriate orientation relative to the brain's neuronal pathways, localized axonal depolarizations are believed to be produced, thus activating the neurons in the relevant brain structure.

Pilot studies evaluating application of rTMS to children and adolescents with both high functioning and low functioning autism have demonstrated reduction of repetitive behaviors and improved social functioning.

- 2) Transcranial Direct Current Stimulation (tDCS): tDCS has been evaluated through clinical trials for numerous neurological applications such as stroke, depression and schizophrenia, wherein its application has been shown to improve certain mental tasks and abilities. tDCS involves application of weak electric current to the brain through the surface of the scalp, such as through use of a 9 volt battery device.

Improvements in various cognitive functions have been consistently demonstrated. Regarding safety, only non-significant side effects have been reported, including a mild tingling and/or itching sensation under the electrode, fatigue after treatment, headache, and insomnia; all of which typically resolve without intervention within 72 hours.

- 3) Acupuncture and Acupressure: Acupressure involves the stimulation of specific acupoints by firm pressure, while acupuncture involves the insertion of very fine needles into the skin at specific acupoints that may be quickly inserted and removed or left in place for some period of time.

The therapeutic effect of acupuncture is based on stimulation at specific acupoints resulting in both local and distant effect via improving signal or modulation of electromagnetic energy

Both acupressure and acupuncture (with or without supplemental electrical stimulation administered through attachments to the handles of the acupuncture needles – Electronic Acupuncture Treatment) have been applied to specific scalp acupoints for various neurological indications including stroke, epilepsy and depression. Improvements in cognitive and behavioral functioning have been consistently reported.

STUDY RATIONALE: Considering a positive study outcome, application of the Erchonia® HLS as proposed in this pivotal trial to reduce the severity of symptoms of autistic disorder, in particular the symptoms of irritability associated with autistic disorder, in children and adolescents aged 5 through 17 years, inclusive, may provide a simple, non-invasive, safe, effective and side-effect free alternative therapy to reduce the severity of symptoms of autistic disorder in affected children and adolescents.

STUDY DESIGN

This clinical study is a double-blind, placebo-controlled randomized parallel group design.

TREATMENT GROUPS

Each subject will be randomized to the test treatment group or to the placebo treatment group, as follows:

- **Test Group:** Subjects randomized to the test group will receive the study treatments with the active (true) Erchonia® HLS device.
- **Placebo Group:** Subjects randomized to the placebo group will receive the study treatments with the 'fake' (placebo) Erchonia® HLS device.

DOUBLE BLIND DESIGN

This clinical study will be a double-blind design, such that neither the subject nor the investigator will be aware of whether a subject has been assigned to the test group or to the control group until after the study is complete.

Maintenance of study double-blind throughout the study duration will be achieved as follows:

- 1) Each subject will be randomly assigned to Treatment Group A or to Treatment Group B. Subjects assigned to Treatment Group A will be treated with the Erchonia® HLS A and subjects assigned to Treatment Group B will be treated with Erchonia® HLS B. Only the study Sponsor will know which label ('A' or 'B') corresponds to the actual (test) HLS device and which label corresponds to the 'fake' device until the final study data analysis is complete. The Sponsor will ensure that this information is stored and maintained confidentially at the Sponsor's work site. This knowledge will not be shared with the investigators, the subjects, or the study Monitor until the final data analysis is complete.
- 2) The fake (placebo) Erchonia® HLS is designed to have the same physical appearance as the actual Erchonia® HLS, including the appearance of any visible light output, and neither the active nor the placebo lasers put out any notable degree of heat or noise. Therefore, there are no distinguishing factors between the active and placebo lasers for subjects or investigators. Additional information on the design, application and proven ineffectiveness of the placebo HLS Laser Device to be used in this study is contained above on pages 10-11 of this protocol document under the section titled: PLACEBO DEVICE INFORMATION.
- 3) There will be two independent investigators interacting with subjects: (i) *administration investigator*: who will be responsible for administering the study treatments; (ii) *assessment investigator*: who will be responsible for recording the study outcome measures. Only the administration investigator will be aware of whether a subject is assigned to Treatment Group A or B, although he or she will not be made aware of whether A or B corresponds to the true or fake laser. Neither the assessment investigator nor the subject will be aware of the subject's A/B Group assignment. In this way, the assessment investigator will not be able to form an association between A/B Treatment Group and active/sham device over the course of the study if a treatment effect is observed.
- 4) During the laser procedures, both the subject and the administration investigator will wear safety glasses that filter out the laser light spectrum. The administration investigator will wear KenTek Corporation KenTek C22-KMT-6101 light blue safety glasses and the subject will wear KenTek Corporation KGOG-6101 light blue Medium Goggles safety goggles. Additional information on this safety eyewear is contained above on pages 6-8 under the section titled: DEVICE SAFETY: RISK AND PREVENTION OF EYE INJURY.

TREATMENT GROUP RANDOMIZATION

Subject allocation to treatment group (A or B) will be via a randomized block design with varying block sizes of two, four and six subjects. In each block, one-half of the subjects will be randomly assigned to Group A and the other half will be randomly assigned to Group B.

Randomization will be attained using computer generation sequence methodology, insuring that the randomization methodology and the generated allocation sequence is concealed from the investigator and subjects.

Concealment will be insured as follows:

- (i) Each computer-generated randomization sequence is unique and will therefore not be able to be replicated.
- (ii) Randomization will occur to either 'Group A' or to 'Group B' rather than to a test or placebo group, and only the designated individual at the study Sponsor's site will know which assignment (A or B) corresponds to the active Erchonia® HLS device and which corresponds to the fake device, with this information not to be revealed until study unblinding that occurs after all data has been entered into the database and the database is sealed prior to statistical analyses.

SUBJECTS

Subjects will be those whose caregivers voluntarily sign the informed consent form, who pass the study qualification evaluation and are subsequently enrolled in the study.

Subject Recruitment

The test site will be responsible for recruitment of its own subjects.

The recruitment process will work as follows:

1. A minor individual has a pre-scheduled appointment at the physician's office (that in the context of this clinical study also functions as the investigator's test site) pertaining to his or her ASD and/or related issues.
2. At the time of this visit, if the physician believes that the patient may satisfy the study qualification criteria (i.e. there are no obvious indicators that may exclude him or her), then the physician will present to the patient's caregiver(s) the option of being a subject in the clinical study.
3. If the patient's caregiver expresses interested in possibly having the minor patient take part in the study, the physician – now in the role of study investigator – will personally review the informed consent form with the individual's caregiver(s) and answer any questions. The individual's caregiver may sign the informed consent form at that visit or he or she may think about it for a while and sign the informed consent form at a later time (taking as long as desired, from hours to days to sign as long as study enrollment is continuing at the time the decision to sign is made), or he or she may refuse to permit the minor child to participate. The Information Sheet for the child/adolescent is also reviewed with the patient, as applicable.
4. Once a caregiver signs the informed consent form, the minor subject will receive a subject ID and proceed to the study qualification evaluation phase of the study.
5. An individual for whom the caregiver decides not to permit participation in the study will continue to work with the physician on the ASD treatment plan goals for the minor patient.

Compensation

A subject or his or her caregiver(s) will not be offered money or any other form of compensation to participate in the clinical study; however, there will also not be any charge for the cost of the study treatments with the Erchonia® HLS laser device or for the cost of any other directly-related evaluations or measurements that occur as part of the subject's participation in this study.

Subject Sample Size

There will be 40 qualified subjects enrolled in this clinical study:

- 20 subjects in the test group
- 20 subjects in the control group

Rationale and Justification for Sample Size

This study is powered to compare one active arm with placebo. Sample size calculation is based on the primary efficacy measure of the mean change from study baseline to endpoint (end of the 4-week treatment period) in the Aberrant Behavior Checklist (ABC) Irritability Subscale score adjusted for the baseline ABC Irritability Subscale score.

Based on detecting a mean difference of -8.5 points between test and placebo groups in the change in ABC Irritability Subscale score adjusted for the baseline ABC Irritability Subscale score being considered clinically relevant with a SD of 8.9, a two-sided test with 80% power and a 5% level of significance, the number of subjects needed per treatment group is 18.

From here, it is anticipated that about one-tenth of subjects overall may withdraw or be terminated from the study prior to completion for various reasons. Therefore, the following formula is used to determine the final needed starting sample size for each procedure arm:

Final sample size = sample size X $1/(1-d)$; where $d = \# \text{ expected dropouts}/\# \text{ subjects enrolled}$.

Final sample size = $18 \times 1/(1-0.11)$; where $d = 2/19$

Final sample size = $18 \times 1/0.89 = 18 \times 1.124 = 20$ subjects per treatment group.

Therefore, a minimum starting sample size of 20 subjects in each treatment group (40 subjects in total) is needed to ensure that a sufficient number remains at study endpoint (18 evaluable subjects per treatment group) for any significant differences found between treatment groups to be considered statistically valid and representative of the general population being sampled.

A detailed rationale and justification as to why these parameters have been selected and determined as statistically significant and clinically meaningful in this pivotal trial with respect to determining sample size is contained below in this protocol document on pages 38 through 40, under the section titled: STATISICAL ANALYSIS PLAN.

STUDY PROCEDURE

STUDY TEST BATTERY

The following is information about the assessment tools that will be used in this study.

- Diagnostic and Statistical Manual of Mental Disorders, 4th Edition, Text Revision criteria (DSM-IV-TR) for autistic disorder

American Psychiatric Association. (2000). Diagnostic criteria for autistic disorder. In Diagnostic and statistical manual of mental disorders (Fourth edition---text revision (DSM-IV-TR). Washington, DC: American Psychiatric Association, 75.

A. A total of Six (or more) items from (1), (2), and (3), with at least two from (1), and one each from (2) and (3):

1. Qualitative impairment in social interaction, as manifested by at least two of the following:
 - marked impairment in the use of multiple nonverbal behaviors such as eye-to-eye gaze, facial expression, body postures, and gestures to regulate social interaction
 - failure to develop peer relationships appropriate to development level
 - a lack of spontaneous seeking to share enjoyment, interest, or achievements with other people (e.g., by a lack of showing, bringing, or pointing out objects of interest)
 - lack of social or emotional reciprocity
2. Qualitative impairments in communication as manifested by at least one of the following:
 - delay in, or total lack of, the development of spoken language (not accompanied by an attempt to compensate through alternative modes of communication such as gesture or mime)
 - in individuals with adequate speech, marked impairment in the ability to initiate or sustain a conversation with others
 - stereotyped and repetitive use of language or idiosyncratic language
 - lack of varied, spontaneous make-believe play or social imitative play appropriate to developmental level
3. Restricted repetitive and stereotyped patterns of behavior, interests, and activities, as manifested by at least one of the following:
 - encompassing preoccupation with one or more stereotyped and restricted patterns of interest that is abnormal either in intensity or focus
 - apparently inflexible adherence to specific, nonfunctional routines or rituals
 - stereotypes and repetitive motor mannerisms (e.g., hand or finger flapping or twisting, or complex whole-body movements)
 - persistent preoccupation with parts of objects

B. Delays or abnormal functioning in at least one of the following areas, with onset prior to age 3 years: (1) social interaction, (2) language as used in social communication, or (3) symbolic or imaginative play.

C. The disturbance is not better accounted for by Rett's Disorder or Childhood Disintegrative Disorder.

➤ Autism Diagnostic Interview, Revised (ADI-R)

The ADI-R is a comprehensive interview used in research settings to provide a thorough assessment of individuals suspected of having autism or other autism spectrum disorders. The ADI-R has proven highly useful for formal diagnosis as well as treatment and educational planning. It is used to support diagnosis or to determine clinical needs

The ADI-R is composed of 93 items and focuses on three functional domains:

- ✓ Language/Communication
- ✓ Reciprocal Social Interactions
- ✓ Restricted, Repetitive, and Stereotyped Behaviors and Interests

Author(s)/developer(s): [name]., FRS, Ann LeCouteur, M.B.B.S., and [name].

Population: Individuals suspected of having autism or other autism spectrum disorders, both children and adults, as long as the individual's mental age is above 2 years, 0 months.

Number of items: 93

Administration/Scoring Time: 1 ½- 2 ½ hours

Administration: To administer the ADI-R, an experienced clinical interviewer questions a parent or caretaker who is familiar with the developmental history and current behavior of the individual being evaluated.

Following highly standardized procedures, the interviewer records and codes the informant's responses. Interview questions cover eight content areas:

- ✓ The subject's background, including family, education, previous diagnoses, and medications
- ✓ Overview of the subject's behavior
- ✓ Early development and developmental milestones
- ✓ Language acquisition and loss of language or other skills
- ✓ Current functioning in regard to language and communication
- ✓ Social development and play
- ✓ Interests and behaviors
- ✓ Clinically relevant behaviors, such as aggression, self-injury, and possible epileptic features

Scoring and Interpretation

Because the ADI-R is an interview rather than a test, and because it focuses on behaviors that are rare in non-affected individuals, it provides categorical results rather than scales or norms. Results can be used to support a diagnosis of autism or to determine the clinical needs of various groups in which a high rate of autism spectrum disorders might be expected (e.g., individuals with severe language impairments or certain medical conditions, children with congenital blindness, and youngsters suffering from institutional deprivation). The ADI-R has proven very effective in differentiating autism from other developmental disorders and in assessing syndrome boundaries, identifying new subgroups, and quantifying autistic symptomatology. Extensive use of the ADI-R in the international research community has provided strong evidence of the reliability and validity of its categorical results.

➤ Aberrant Behavior Checklist (ABC)

The ABC is a 58-item symptom checklist for assessing and classifying problem behaviors of children, adolescents and adults with mental retardation and developmental handicaps at home, in residential and treatment facilities, and community and educational settings. It is also used as an assessment of pharmaceutical and other treatment effects on children, adolescents and adults. The ABC was empirically developed by factor analysis on data from 1,000 individuals.

The 58 items resolve into five subscales:

1. Irritability and Agitation (15 items)
2. Lethargy and Social Withdrawal (16 items)
3. Stereotypic Behavior (7 items)
4. Hyperactivity and Noncompliance (16 items)
5. Inappropriate Speech (4 items)

The Irritability Subscale includes questions about aggression, self-injury, tantrums, agitation and unstable mood on a scale of 0 to 45, with higher scores indicating greater severity. Data from studies of developmentally disabled children indicated that a score of 18 is 1.3 to 1.5 SD above the population means, depending on the age and sex of the child.

Author(s)/developer(s): Aman, M.G., Sing, N.N., Stewart, A.W., & Field, C.J.
Date of publication: 1985
Population: Developmentally handicapped children, adolescents and adults aged 5-58.
Number of items: 58
Administration Time: 10-15 minutes
Method of administration: Teacher or parental observational report; may also be completed by health care practitioners or mental health professionals.
Respondent(s): Parents, teachers, health care providers, medical/mental health professionals.

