- Subjects must agree to not change or start taking any new medications, or partake in any other new treatments, or to change the dosages they take of current medications, to treat the symptoms of autism disorder, during the course of study participation.
- Subjects must agree to notify the study investigator immediately if their treating physician makes any change to medication or dosage.
- Females of child-bearing age must agree to use acceptable means of contraception, as detailed in the study qualification evaluation section.

STUDY TREATMENT ADMINISTRATION PROTOCOL

- The study treatment administration phase will extend over four consecutive weeks.
- Each subject will receive a total of eight study treatments with the Erchonia® HLS laser device, two treatments per week for 4 consecutive weeks, each treatment administration 3 to 4 days apart.
- Each study treatment will be administered by the study investigator at the study test site.
- Each study treatment administration will last 5 minutes.

Erchonia® HLS Treatment Administration Protocol

The treatment administration process is as follows:

1. The subject is seated comfortably.
2. The administration investigator puts on the KenTek Corporation KenTek C22-KMT-6101 light blue safety glasses.
3. The subject is correctly fitted with the KenTek Corporation KGOG-6101 light blue Medium Goggles safety goggles.
4. The Erchonia® HLS laser is applied four inches from the skin surface, and the laser light is directed perpendicular to the plain of the skin ensuring that the beam is penetrating perpendicular to the skin.
5. Pulsed laser therapy 8, 53, 73 and 101 is applied systematically to the base of the brain and temporal areas for 5 continuous minutes.
6. The HLS laser is turned off.
7. The administration investigator removes the safety glasses and the subject removes the safety goggles.
8. The treatment session is complete.

STUDY EVALUATION TIMELINE

The study evaluation phase is as follows:

- ✓ Treatment Administration Phase: 4 weeks
- ✓ Post-treatment Evaluation Phase:
 - 4 weeks for all subjects
 - 6 months for subjects who had been assigned to the active treatment group

The evaluation time points and associated measures to be evaluated during the course of this study are as follows:

TREATMENT ADMINISTRATION PHASE: 4 WEEKS

At Each of the 8 Study Treatment Administration Visits

- Medication and therapy use review
- Adverse events evaluation

WEEK 2 END: Study Midpoint

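### Two fixed device labels, known child by child to the person giving treatment, leave that person able to infer the active label if the device works; the plan closes this route only for the assessor

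*Combined protocol and SAP*

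**What the plan says.** Item 1 of the Double Blind Design section sets up two labels for the whole trial: "Subjects assigned to Treatment Group A will be treated with the Erchonia® HLS A". A second device, labelled B, serves the other group in the same way. One key links label to device, and it is held centrally: "Only the study Sponsor will know which label ('A' or 'B') corresponds to the actual (test) HLS device".

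Item 3 separates two roles. The administration investigator gives the treatments and the assessment investigator records the outcomes. On the labels, "Only the administration investigator will be aware of whether a subject is assigned to Treatment Group A or B", with the safeguard that "he or she will not be made aware of whether A or B corresponds to the true or fake laser". For the others, "Neither the assessment investigator nor the subject will be aware of the subject's A/B Group assignment". The stated purpose concerns the case where an effect shows: the assessor then "will not be able to form an association between A/B Treatment Group and active/sham device over the course of the study".

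Treatment is given at 8 visits over 4 weeks. The Study Evaluation Timeline also places a "Medication and therapy use review" and an adverse event evaluation at each of these visits, without saying which investigator does them. The secondary outcome section bases the responder criterion on the primary caregiver's rating of the same ABC Irritability Subscale that is the primary measure.

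**The concern.** Every active child shares one letter and every placebo child shares the other, so impressions of individual children can be pooled by letter. The plan's reason for keeping the letters from the assessor applies equally to the administration investigator, who holds the letters and meets the children repeatedly. That person's only stated protection is not being told the key. Matching the devices on appearance, light, heat and noise does not prevent inference from how the children are doing.

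The ABC is rated by caregivers. No section limits what the administration investigator may hear from caregivers or say to them, and none bars that person from the outcome records, which are kept in each child's single file at the site (Subject Privacy and Confidentiality). If the active label were inferred, expectation could reach the raters. The opportunity for this grows when the device appears to work.

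**Working it through.** **Inputs.** From the sample size rationale: difference 8.5 points, SD 8.9, two-sided 5%, 80% power, 18 evaluable per group, 40 enrolled. From the randomisation section: equal allocation in blocks of 2, 4 and 6, so both labels appear from the start. From the ABC description: inter-rater reliability 0.17 to 0.90, mean 0.60.

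**The plan's own figure.** n per group = 2 × (1.960 + 0.842)² × (8.9/8.5)² = 2 × 7.85 × 1.096 = 17.2, rounded up to 18. This agrees with the plan.

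**Chance that the better-looking label is the active one.** The standardised effect is d = 8.5/8.9 = 0.955. After k completed children per label, the probability that the active label has the better mean is Φ(r × d × √(k/2)). Here r is the assumed correlation between what the administration investigator perceives and the ABC change. The documents give no value for r. The case r = 1 means perception as good as the ABC itself; r = 0.6 borrows the mean inter-rater reliability as a guide.

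Worked for k = 3:
- r = 1: Φ(0.955 × 1.225) = Φ(1.170) = 0.88.
- r = 0.6: Φ(0.6 × 1.170) = Φ(0.702) = 0.76.

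| Scenario | k = 3 | k = 5 | k = 10 |
|---|---|---|---|
| Planned effect, r = 1 | 0.88 | 0.93 | 0.98 |
| Planned effect, r = 0.6 | 0.76 | 0.82 | 0.90 |
| Planned effect, r = 0.3 | 0.64 | 0.68 | 0.74 |
| Half the effect (4.25), r = 1 | 0.72 | 0.77 | 0.86 |

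A simulation with the plan's block sizes agreed. At r = 1 it gave 0.91 after 8 children in total, 0.95 after 12 and 0.98 after 20. At r = 0.6 it gave 0.79, 0.84 and 0.90.

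**How many children come after the guess.** This depends on accrual. The tenth child finishes 4 weeks of treatment at these points, for assumed rates:
- 1 per week: week 10 + 4 = 14, with 14 enrolled and 26 still to start.
- 2.5 per week: week 4 + 4 = 8, with 20 enrolled and 20 still to start.
- 10 per week: week 1 + 4 = 5, with all 40 enrolled and none still to start.

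**Contrast with child-specific codes.** Nothing can be pooled by code. Even at r = 1, the best guess for a single child is right with probability Φ(0.955/2) = Φ(0.478) = 0.68, however many children have been treated. One disclosure then reveals 1 child of 40.

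**The case against.** The plan has real safeguards: matched devices, filtering eyewear, a separate assessor, and a key withheld even from the Monitor. Four stronger readings are tempting, and the documents do not support them.

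- *One disclosure unblinds the whole trial.* Learning that A is active reveals a child's arm only to someone who also holds that child's letter. The plan gives the letters to the administration investigator and withholds them from the assessor and subjects. A leaked key therefore decodes all 40 children for the label-holder, and a second leak would be needed for anyone else.
- *The code is in practice known early, and about 30 of 40 children are treated afterwards.* This needs perception as accurate as the ABC, from someone who does not record outcomes. It also needs the first ten children to finish before the eleventh starts. No accrual rate is given, so 30 is a ceiling and not an expected number.
- *Co-treatment and adverse event records will be collected differently by arm.* The plan does not say who does the reviews at treatment visits, so this is only a possibility.
- *One person gives every treatment.* Item 3 uses the singular, but the confidentiality section refers to test sites in the plural. With several administrators, each would see fewer children per label.

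It is also fair that a probability of a correct guess is not a bias. The step from a guess to an altered rating is plausible but cannot be measured from the documents. These points limit the size of the concern. They leave the gap itself: the plan names an inference route and closes it for one of the two people concerned.

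**Conclusion.** The concern holds as a design weakness of limited and uncertain size. Two labels cover the whole trial, the administration investigator knows each child's label, and the protection against linking label to device extends only to the assessor. At the planned effect, the chance that the better-looking label is the active one ranges from about 0.76 (r = 0.6) to at most 0.88 (r = 1) after 3 children per label, and from 0.90 to 0.98 after 10. Lower values follow from weaker perception or a smaller effect. These figures assume approximately normal changes with the plan's SD and some informal view of how the children are doing.

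A reader might infer that the blind will fail or that the primary result will be biased. The documents support neither. They show an avoidable opportunity for bias in a caregiver-rated outcome, in a pivotal trial meant to support a marketing application, and it is worth closing because this is cheap.

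**What to change.** In items 1 and 3 of the Double Blind Design section, and correspondingly in the randomisation section:

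- Replace labels A and B with several non-informative device codes per arm, or with child-specific codes. Assign them through the randomisation list, with only the sponsor's key-holder able to map code to arm.
- State that the administration investigator only operates the device, does not discuss progress or expectations with caregivers, and does not see the ABC or CGI records.

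The cost is a few more labelled units, some device logistics and a wording change. Sample size and primary analysis are unaffected. Several codes per arm protect only in part: with three per arm, for example, one disclosure would still reveal the children on that code, about 20/3 ≈ 7, to whoever holds the codes. Child-specific codes limit it to one child.

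The assessment investigator should not be added to the treatment visits. That would mean up to 8 × 40 = 320 extra contacts and would bring the assessor into sessions with the label-holder, weakening the separation that item 3 creates.
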